5.4.3 Storage re-use, and destruction of pharmacodynamic samples

The primary pharmacodynamic (PD) samples will be kept in the AZ Biobank for 15 years for future needs.

Samples will be stored for a maximum of 15 years from the date of the Last Subject's Last Visit, after which they will be destroyed. The results of any investigation will be reported either in the Clinical Study Report itself or as an addendum, or separately in a scientific report or publication.

5.5 Biomarker analysis

The patient's consent to the use of donated biological samples is mandatory.

Biological samples (e.g., archived tumour samples) will be collected and may be analysed for exploratory biomarkers to assess correlations with disease activity, effects of study drug, clinical outcomes and toxicity.

Details on sample processing, handling, and shipment are provided in the Laboratory Manual.

The results of exploratory biomarker research will be reported separately and will not form part of the CSR.

5.5.1 Exploratory biomarker research – Part A and Part B

Blood samples for plasma ctDNA and cytokine collections will be taken at the times presented in [Table 1](#) and [Table 2](#). Specifically at the following times:

- Before the first dose of AZD1775
- Cycle 1 Day 15
- Cycle 2 Day 1 pre-dose
- Cycle 2 Day 8, 2-4 hours post first dose of day
- Cycle 4 Day 1 pre-dose
- Cycle 6 Day 1 pre-dose
- Day 1 every 2 cycles after completing Cycle 6. Patients continuing study treatment for a minimum of 1 year may have the ctDNA and cytokine collection expanded to every 4 cycles (12 weeks [± 7 days]).

- At disease progression (AZD1775 discontinuation)

For patients continuing on AZD1775 after the implementation of the Revised Clinical Study Protocol Version 5, DNA blood samples (2 x 10 mL) for future biomedical research should be obtained at the time of AZD1775 discontinuation if due to disease progression (unless informed otherwise by AstraZeneca). The samples will be processed on site, as per the laboratory manual, to yield plasma for analysis of oncology biomarkers which may correlate with drug response or resistance, including analysis of circulating tumour DNA.

Details on sample processing, handling, and shipment are provided in the Laboratory Manual.

The results of exploratory biomarker research will be reported separately and will not form part of the CSR.

5.5.2 Whole blood collections for immune profiling flow cytometry

Whole blood samples will be collected from for immune profiling flow cytometry in all Part A patients and Part B ovarian cancer patients as follows:

- Baseline (within 2 weeks of initiation of dosing)
- Cycle 1 Day 1 pre-dose
- Cycle 1 Day 15
- Cycle 2 Day 1 pre-dose
- Cycle 2 Day 8, 2-4 hours post first dose of the day (Part B patients only)
- Cycle 4 Day 1 pre-dose

The flow cytometry sample assessment may include but is not limited to activated and memory T cells, proliferating T cells, surface Treg, TBNK and MDSCs. These sample collections have unique shipping requirements which are detailed in the Laboratory Manual along with the sample processing and handling requirements.

The results of this research will be reported separately and will not form part of the CSR.

5.5.3 Storage, re-use and destruction of biological samples

Samples will be stored for a maximum of 15 years from the date of the Last Subject's Last Visit, after which they will be destroyed. The results of this biomarker research will be reported either in the Clinical Study Report itself or as an addendum, or separately in a scientific report or publication. The results of this biomarker research may be pooled with biomarker data from other studies with the study drug to generate hypotheses to be tested in future research.

5.5.4 Tumour-derived and plasma circulating tumour DNA samples

Details of sample collection, processing, shipping, and storage will be described in the Laboratory Manual.

The processes adopted for the coding and storage of samples for genetic analysis are important to maintain subject confidentiality. Samples will be stored for a maximum of 15 years from the date of the Last Subject's Last Visit, after which they will be destroyed. DNA is a finite resource that may be used up during analyses. Samples will be stored and used until no further analyses are possible or the maximum storage time has been reached.

For all samples irrespective of the type of coding used the DNA will be extracted from the blood or other appropriate sample type. The DNA sample will be assigned a unique number replacing the information on the sample tube. Thereafter, the DNA sample will be identifiable by the unique DNA number only. The DNA number is used to identify the sample and corresponding data at the AstraZeneca genetics laboratories, or at the designated contract laboratory. No personal details identifying the individual will be available to any person (AstraZeneca employee or contract laboratory staff working with the DNA.)

The samples and data for genetic analysis in this study will be single coded. The link between the subject enrolment and the DNA number will be maintained and stored in a secure environment, with restricted access within the Laboratory Information Management System (LIMS) at AstraZeneca. The link will be used to identify the relevant DNA samples for analysis, facilitate correlation of genotypic results with clinical data, allow regulatory audit and to trace samples for destruction in the case of withdrawal of consent when the subject has requested disposal/destruction of collected samples not yet analysed.

5.5.5 Archived or recent tumour tissue

A sufficient quantity of archival or fresh tumour tissue must be available to enrol a patient to Part B to identify molecular biomarkers of interest. Molecular biomarker assessments will be performed centrally from archival tumour tissue or from fresh tumour tissue if the latter is being taken for routine clinical purposes and archival tumour tissue is unavailable.

After signing a 'pre-screening' ICF, tumour samples will be submitted for a pathology QC check to ensure that the molecular analysis will be possible with the material provided. If the tumour tissue sample does not pass the QC check, the investigative site will be informed and additional tissue will be requested.

The patients' molecular profiles will be established using a Sponsor-approved method and clinical laboratory (see Laboratory Manual).

All tumour samples will be analysed for a range of cancer-related genes such that clinical response can be correlated to the gene aberrations. TNBC and SCLC biomarker 'positive' cohorts to be analysed include amplifications in CCNE1, MYC, MYCN, or MYCL1.

Biomarker 'negative' is defined as the absence of the qualifying amplification for TNBC or SCLC as specified above. Investigation of biomarker 'negative' results based on emerging signals may be explored through additional expansion cohort(s).

Patients may not have to wait for confirmation of the pathology QC check if genetic profile results are available to confirm the specific biomarker of interest (i.e., *BRCA1* or *BRCA2* genes in ovarian cancer, amplification *CCNE1*, *MYC*, *MYCN*, or *MYCL1* in TNBC or SCLC). The results must be from a certified laboratory and approved by the Sponsor or designee on a case-by-case basis. Submission of archived or fresh tumour tissue to the Central Laboratory will be required. If the tumour sample is considered insufficient by the pathology QC check at the time of analysis the patient will remain on-study.

The preferred tumour tissue samples are block(s) rather than slides, with minimum tumour attributes of $\geq 10\text{mm}^2$ surface area; $\geq 30\%$ tumour cell content, if biopsy, ideally a block contains multiple cores. If a block is unavailable, unstained $5\mu\text{m}$ sections should be provided as follows:

- Large resection >10 slides
- Small biopsy (core needle, bronchial, FNA, effusions) $>15-20$ slides

Please refer to the Laboratory Manual for additional guidance.

Gene expression profiling (GEP) technology, next generation sequencing (NGS) and immunohistochemical (IHC) analysis will be used to identify the mutations of interest.

A full report of the molecular biomarker panel will subsequently be made available to investigators upon request. Refer to the Investigator Laboratory Manual for instructions.

Details of sample collection, processing, storage, and shipment are provided in the Laboratory Manual.

5.5.6 On-treatment tumour biopsy (surface-accessible lesion)

An on-treatment tumour biopsy is required for all patients with surface-accessible lesions, at any time, 12 hours after the third administered dose of AZD1775 on Day 2, or later on Day 3, or during the first 12 hours on Day 4 of Cycle 1 unless medically contraindicated in the opinion of the Investigator.

This biopsy is needed to demonstrate that there is a measurable decrease from baseline in readouts of activity of the Wee1 kinase via analysis of the levels of phosphorylated CDC2 (pCDC2) in tumour samples, following treatment with AZD1775. The collection of baseline and on-treatment biopsies is essential to guarantee the comparison of pCDC2 levels before and during treatment and to provide evidence that patients receive a biologically active dose.

A 'surface accessible lesion' is a lesion that does not require the patient to undergo general anaesthesia for the biopsy procedure, does not require CT-guided interventional radiology involvement and could, for example, be a clearly palpable tumour-involved node or similar.

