- t Dispense AZD1775 at the beginning each new treatment cycle, and review and document AZD1775 dosing compliance with the patient at each visit. AZD1775 BID Days 1-3 and 8-10 of each treatment cycle. AZD1775 should be taken with 8 ounces of water approximately 2 hours before and again 2 hours after food. Note: the AZD1775 BID starting dose is reduced to 175 mg (Days 1-3, week 1 and week 2 of each 21-day cycle) because 200 mg BID was not well-tolerated.
- u Optional tumour biopsies (from the primary tumour or metastatic site) will be collected from consenting patients including those that continue after FPV, with easily accessible tumours (see Section 5.5.5). Tumour samples may be collected pre-dose at screening or baseline and at the time of disease progression. This sample is **optional** and must be taken from patients who have provided informed consent for tumour biopsies. All tumour biopsies will be collected, stored, and shipped as detailed in the Investigator Laboratory Manual.
- v When applicable, tumour markers that are elevated and are used by the Investigator to monitor for tumour response will be collected at baseline, Day 1 of each cycle and at the end of treatment. The tumour marker analysis will be performed by a local laboratory.
- w Previous individual patient genomic profile reports should be provided for this study at enrolment.
- x Whole blood samples for PBMC analysis (see Section 5.4.1) are to be collected from all ovarian cancer patients in Part B. Samples are to be collected on Cycle 1 Day 1 and Day 8 pre-dose, Cycle 2 Day 8, 2-4 hours after dosing, and Cycle 4 Day 1 pre-dose.
- y All patients must receive a 5-HT₃ antagonist, ondansetron (Zofran) 8 mg PO BID or granisetron (Kytril) 1 mg PO BID prior to each dose of AZD1775. In addition, dexamethasone 4 mg PO will be given with each AZD1775 dose as a minimum on the first day of dosing AZD1775 of every 3-5 days dosing period, unless contraindicated or not well-tolerated. Dexamethasone or the 5-HT₃ antagonist may be given by IV. Promethazine (Phenergan), prochlorperazine (Compazine), and benzodiazepine may still be used as additional adjunctive treatments during AZD1775 therapy. Please note: aprepitant [Emend] and fosaprepitant are not permitted due to known drug-drug interactions. Patients should be strongly encouraged to maintain liberal oral fluid intake.

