5.4.2 Repeat biopsies

Part B of the study is designed in part to provide evidence of proof of mechanism (POM). For the Wee1 inhibitor AZD1775, this means to demonstrate that following treatment of patients there is a measurable decrease from baseline in readouts of activity of the Wee1 kinase.

The baseline Wee1 pharmacodynamic (PD) marker pCDK1 (pCDC2) will be retrospectively assessed from the baseline biopsy. A post-treatment biopsy will then be taken after first dose on day 2 or day 3 of the first cycle of treatment.

These paired biopsies will be considered evaluable for POM if assessable by Immunohistochemistry (IHC) for the biomarker above and if the concurrent pharmacokinetic (PK) blood sample is consistent with the patient having had adequate pharmacological exposure to AZD1775.

We estimate that we would need at least 7 patients with evaluable paired biopsies in order to have confidence in an assessment of POM (see statistical calculations below).

A patient showing the target decrease of 50% or more (evaluated as number of cells showing positive staining in post vs pre dose) in pCDK1 will be considered a pharmacodynamic responder. This value is based on preclinical data correlating with anti-tumour efficacy, using the same assay to be used on clinical samples. We have set a POM target value of 50% of

patients having a pharmacodynamic response in their tumour biopsy. With n=7 biopsies, we would accept having established POM if 4 out of the 7 biopsies show the desired biomarker change.

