5.5.7 Optional biopsies

Optional during this study and will be requested from consenting patients with easily accessible tumours:

- At baseline/screening before dosing
- At the time of disease progression including from consenting patients that continue treatment after the FPV.

Patients will sign a separate informed consent for the tumour tissue biopsies. The tumour biopsy procedure will be performed by core needle, under radiological guidance, or surgically if the site of disease is superficial and palpable or visible. It is mandated that the core biopsy be removed directly from the tumour *in situ* and not cored from a surgically removed tumour. This is to ensure the best possible quality of the biopsy, as the blood/nutrient supply to the tumour is not disrupted prior to biopsy collection.

All tumour biopsies will be collected, stored, and shipped as detailed in the Laboratory Manual.

Any residual samples remaining after analysis will be retained for any potential subsequent retrospective analysis of other response related and/or cancer related biomarkers. It is not intended that data derived from residual sample analysis will be reported in the CSR.

Informed consent must be obtained from any patient who agrees to provide tissue for tumour tissue sample testing.

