8.9 Pharmacokinetics/Pharmacodynamic Analysis

The plasma concentration data for AZD1775 may be analysed using a population PK approach, which may include exploring the influence of covariates on PK, if the data allows. A population pharmacodynamics approach will be used to investigate the relationship between PK and selected primary, secondary and/or exploratory endpoints, where deemed appropriate. Results may be reported separately from the CSR for the main study. The PK, pharmacodynamics, demographic, safety and tumour response data collected in this study may also be combined with similar data from other studies and explored using population pharmacokinetic and/or pharmacokinetic-pharmacodynamics methods. The results of any such analyses will be reported separately from the CSR.

Pharmacodynamic response

At least 7 patients (any tumour type acceptable) should consent to and complete the optional paired biopsy testing for this response to be evaluated. The target response rate is defined as 50% with a value of 25% being considered too low to be of interest. Assuming the probability of a false positive and a false negative to be 20% and 10% respectively, if 4/7 patients respond then we can conclude that the response rate is greater than 25% and consistent with 50% (lower boundary one sided 80% CI = 35%). However, if 1/7 patients respond then we do not have sufficient evidence that the response rate is 50% (upper boundary one sided 90% CI = 45%). For information with 4/7 (57%) responders the exact 2-sided 80% confidence interval would be (27%, 83%).

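### The on-treatment biopsy is required where a lesion is surface-accessible, but the pre-dose biopsy it must be compared with is optional, and the pCDK1 baseline sample is not defined

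*Protocol*

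**What the plan says.** **On-treatment biopsy.** Section 5.5.6 states: "An on-treatment tumour biopsy is required for all patients with surface-accessible lesions". The window runs from Day 2 to Day 4 of Cycle 1, with an exception for medical contraindication in the investigator's opinion. Table 2 footnote z carries the same rule for Part B.

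**Pre-dose biopsy.** Section 5.5.7 introduces its biopsies with "Optional during this study and will be requested from consenting patients with easily accessible tumours", lists "At baseline/screening before dosing" among the time points, and asks for separate consent. Table 2 footnote u is also permissive: "Tumour samples may be collected pre-dose at screening or baseline and at the time of disease progression". Under Section 3.3, a patient who refuses the optional biopsies suffers no penalty and stays in the rest of the study.

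**Purpose.** Section 5.5.6 gives the reason for the on-treatment sample: "The collection of baseline and on-treatment biopsies is essential to guarantee the comparison of pCDC2 levels before and during treatment". Under Section 5.4.2 the baseline marker "will be retrospectively assessed from the baseline biopsy", a responder has a fall of at least 50% in positively staining cells, and proof of mechanism needs "at least 7 patients with evaluable paired biopsies".

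**Statistical section.** Section 8.9 says that at least 7 patients "should consent to and complete the optional paired biopsy testing for this response to be evaluated".

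**Other pre-treatment tissue.** Inclusion criterion 15 and Section 5.5.5 require tissue for molecular profiling. It is archival, or fresh if archival tissue is unavailable and fresh tissue is being taken in routine care.

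**The concern.** The procedure that can be enforced is the second half of a comparison whose first half is voluntary. No section makes the on-treatment biopsy depend on a pre-dose sample. A site that follows the text would take an invasive research biopsy from a patient for whom the stated purpose, a change from baseline, cannot be met.

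The second problem is the baseline sample. Section 5.4.2 speaks of a baseline biopsy without saying whether this is the optional fresh biopsy, recent routine-care tissue or the archival block supplied for enrolment. All patients have had chemotherapy for recurrent or metastatic disease (inclusion criterion 3), so an archival block may predate that therapy and may come from a different lesion. A 50% difference between such a block and an on-treatment biopsy would not isolate the effect of AZD1775.

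Third, 5.5.6 and 8.9 disagree on whether the on-treatment biopsy is required or optional, so a site cannot tell which consent applies.

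**Working it through.** **Step 1. The plan's own figures.** With exact (Clopper-Pearson) bounds for 7 pairs:

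| Quantity | Stated in 8.9 | Recomputed |
|---|---|---|
| 4/7, one-sided 80% lower bound | 35% | 35.0% |
| 1/7, one-sided 90% upper bound | 45% | 45.3% |
| 4/7, two-sided 80% interval | 27% to 83% | 27.9% to 83.0% |

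The figures reproduce, apart from a trivial rounding of the last lower limit. Under the rule of at least 4 of 7, the chance of passing is 7.1% if the true response rate is 25% and 50.0% if it is 50%. All of this presupposes 7 complete pairs. With a threshold of 4 of 7, reclassifying one patient turns 4/7 into 3/7 and reverses the call, so the choice of baseline sample matters.

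**Step 2. The rules side by side (Part B, surface-accessible lesion, no contraindication).**

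| Pre-dose sample | On-treatment biopsy under 5.5.6 | Valid pCDK1 change? |
|---|---|---|
| 5.5.7 biopsy accepted | Required | Yes, if evaluable |
| Declined, but recent routine-care tissue exists | Required | Possibly; the protocol does not say |
| Declined, only archival tissue taken before intervening therapy | Required | No |

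The third row is the defect. The second and third rows show the gap in 5.4.2.

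**Step 3. Size.** Let N be the number of patients biopsied on treatment and p the share of them with a usable baseline.

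- Unpaired biopsies = N(1-p)
- Pairs before evaluability losses = Np

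The protocol gives neither N nor p. Taking p as an assumption, the unpaired share 1-p is:

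| p (assumed) | 1-p |
|---|---|
| 0.90 | 10% |
| 0.75 | 25% |
| 0.50 | 50% |
| 0.25 | 75% |

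N cannot exceed the Part B maximum of 160 (Section 8.1). The proportion with surface-accessible lesions is not stated, so no count follows. Section 5.4.2 also requires that the pair be assessable by IHC and that the concurrent PK sample show adequate exposure, so evaluable pairs will be at most Np.

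**The case against.** **The text can be read as conditional.** Section 5.4.2 describes a sequence in which the baseline is followed by a post-treatment biopsy, 5.5.6 calls both samples essential, and 8.9 speaks of patients who consent to the pair. This shows the likely intent. It does not override the plain requirement in 5.5.6 and footnote z, which names no such condition.

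**Some patients will have another pre-dose sample.** Sections 3.3 and 5.5.5 allow fresh routine-care tissue, and 5.5.5 already includes IHC on the enrolment tissue. This stands. A reader might infer that every required on-treatment biopsy is unusable, and the documents do not support that. The loss is confined to patients without a usable pre-dose sample.

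**The contraindication exception softens the requirement.** It does, but on grounds of medical risk, not of a missing baseline.

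**A count is tempting but not available.** A reader might divide 7 by an assumed uptake to obtain the number of biopsies needed and the number wasted. That assumes collection stops at the seventh pair. The protocol has no such stop: the requirement covers all qualifying patients, and 5.4.2 asks for at least 7.

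**Archival tissue may never be used.** The protocol does not plan to use it as the pCDK1 baseline. Nor does it exclude it, so a biased proof-of-mechanism call is a possibility left open, not a predicted result.

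**The stakes are limited.** Proof of mechanism is in none of the objectives in Section 2 and does not affect ORR, DCR, DoR or PFS. This stands, although 5.4.2 says Part B is designed partly for it.

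**Conclusion.** The concern holds in a bounded form. Sections 5.5.6, 5.5.7 and 8.9 and footnotes u and z do not agree on which biopsies are required, and 5.4.2 leaves the pCDK1 baseline sample undefined. As written, some patients can undergo a required research biopsy that supports no valid pre/post comparison. Their number is N(1-p), with both terms unknown.

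A reader might go further and conclude that the proof-of-mechanism assessment is invalid. The documents do not support this: pairs with a fresh pre-dose sample remain sound, and the binomial figures in 8.9 are correct to rounding.

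The conclusion rests on the current text being applied literally. The protocol does not say whether Part B enrolment is complete. If it is, the biopsy requirement no longer affects new patients, but the choice of baseline sample and the conflict between 5.5.6 and 8.9 still matter for analysis and reporting. This is a cheap improvement worth making. It does not threaten the primary endpoints.

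**What to change.** 1. In Section 5.5.6 and Table 2 footnote z, make the on-treatment biopsy conditional on a usable fresh pre-dose sample: the 5.5.7 biopsy, or recent routine-care tissue taken after the last prior therapy. Ask for the same lesion where possible. Keep the contraindication exception.
2. In Section 5.4.2, state which samples qualify as the pCDK1 baseline, and that archival tissue taken before intervening therapy does not.
3. Align Section 8.9 with 5.5.6, so that both give the same status to each half of the pair.

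The cost is an amendment and matching consent wording. No biopsy is added, and on-treatment biopsies without a usable baseline are no longer taken. The downside is that a patient who declines the optional pre-dose biopsy would then usually avoid the on-treatment one as well, which may lower uptake. The number of evaluable pairs should therefore be tracked during enrolment against the required 7.
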